5 STUDY DESIGN

5.1 Overall Design

[figure not shown]
This is a Phase 2, randomized, open-label, 2-arm study of BMS-986213 or nivolumab in combination with investigator's choice chemotherapy as L1 treatment in participants with untreated, unresectable, and either locally advanced or metastatic GC or GEJ adenocarcinoma. Approximately 250 participants will be randomized in 2 treatment arms in this global clinical study. Nivolumab monotherapy will be administered IV as either 360 mg every 3 weeks (Q3W) or 480 mg every 4 weeks (Q4W), depending on the assigned chemotherapy regimen. Relatlimab and nivolumab combination, as an FDC, will be administered as 120-mg relatlimab/360-mg nivolumab Q3W or 160-mg relatlimab/480-mg nivolumab Q4W, depending on the assigned chemotherapy regimen.

After signing the informed consent form, participants will enter the Screening Phase. A pre-treatment tumor sample is required to be submitted from all participants. Although this study will enroll participants regardless of their LAG-3 expression status ($\geq 1\%$ or $< 1\%$; no indeterminate allowed), participants must have their LAG-3 status determined prior to completion of the remaining Screening procedures. **Patients with an indeterminate LAG-3 expression status cannot be enrolled in the study.** As deemed appropriate by the Investigator, participants may complete the remaining Screening procedures in parallel to the determination of the LAG-3 status in order to minimize the duration of the Screening Phase.

The study design schematic is presented in [Figure 5.1-1](#).

Figure 5.1-1: Study Design Schematic

^a Fixed dose combination of relatlimab [anti-LAG-3] plus nivolumab

^bInvestigator Choice Chemo:

1. **XELOX:** oxaliplatin 130 mg/m² administered IV on Day 1 of each treatment cycle and capecitabine 1000 mg/m² administered orally twice daily on Days 1 to 14 of each treatment cycle, every 3 weeks
2. **FOLFOX:** oxaliplatin 85 mg/m², leucovorin 400 mg/m² and fluorouracil 400 mg/m² administered IV on Day 1 of each treatment cycle, and fluorouracil 1200 mg/m² IV continuous infusion over 24 hours daily or per local standard on Days 1 and 2 of each treatment cycle, every 2 weeks.

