7.1.2 Dose Schedule for BMS-986213 or Nivolumab Plus XELOX

Participants assigned to XELOX will receive BMS-986213 (relatlimab 120 mg/nivolumab 360 mg) or nivolumab 360 mg, administered IV over 60 minutes or 30 minutes, respectively, oxaliplatin 130 mg/m² administered IV on Days 1 and 22 of each 6-week treatment cycle, and

capecitabine 1000 mg/m² administered orally twice daily (ie, 1000 mg/m² in the morning and 1000 mg/m² in the evening) on Days 1 to 14 and Days 22 to 35 of each 6-week treatment cycle (see Table 7.1.2-1). Immunotherapy treatment should be administered first, prior to chemotherapy treatment. Dosing windows for subsequent XELOX doses should adhere to recommendations in the prescribing information or local standards, where indicated.

Premedication for potential infusion reaction is not recommended for the first dose of either treatment. Premedication maybe administered for nausea and vomiting prophylaxis, after the completion of the immunotherapy treatment or, in the absence of preceding immunotherapy, before chemotherapy administration, as clinical presentation warrants and per local standard.

Capecitabine should be taken with food.

Participants should be provided with drug diaries at each visit and instructed to record intake of capecitabine in the diary after each twice daily administration.

Table 7.1.2-1: Dose Schedule for BMS-986213 or Nivolumab Plus XELOX

Treatment Group	Drug Name	Cycle 1 (Week 1)	Cycle 2 (Week 7)	Cycle 3 (Week 13)	Cycle 4 (Week 19)	Cycle 5 (Week 25) until EOT (Every 6 weeks)
BMS-986213 or nivolumab in combination with XELOX	BMS-986213 (relatlimab 120 mg/nivolumab 360 mg), nivolumab 360 mg	Days 1 and 22	Days 1 and 22	Days 1 and 22	Days 1 and 22	Days 1 and 22
	Oxaliplatin 130 mg/m ²	Days 1 and 22	Days 1 and 22	Days 1 and 22	Days 1 and 22	Days 1 and 22
	Capecitabine 1000 mg/m ² twice daily (ie, 1000 mg/m ² in the morning and 1000 mg/m ² in the evening)	Days 1 to 14 and Days 22 to 35	Days 1 to 14 and Days 22 to 35	Days 1 to 14 and Days 22 to 35	Days 1 to 14 and Days 22 to 35	Days 1 to 14 and Days 22 to 35

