7.3.3.2 Dose Modification Criteria for XELOX

Capecitabine

Toxicity due to capecitabine administration may be managed by symptomatic treatment and/or treatment interruption or dose reduction. Dose modifications of capecitabine are presented in Table 7.3.3.2-1. Once the dose has been reduced, it should not be increased at a later time. For those toxicities considered by the treating physician to be unlikely to become serious or life threatening (eg, alopecia, altered taste, or nail changes), treatment can be continued at the same dose without reduction or interruption. Participants taking capecitabine should be informed of the need to interrupt treatment immediately if moderate or severe toxicity occurs. Doses of capecitabine omitted for toxicity are not replaced.

Table 7.3.3.2-1: Recommended Dose Modifications of Capecitabine

Toxicity ^a	During a Course of Therapy	Dose Adjustment for Next Treatments (% of starting dose)
Grade 1	Maintain dose level	Maintain dose level
Grade 2		
1st appearance	Interrupt until resolved to Grade 0 to 1	100% (1000 mg/m ²)
2nd appearance		75% (750 mg/m ²)
3rd appearance		50% (500 mg/m ²)
4th appearance	Discontinue treatment permanently	-
Grade 3		
1st appearance	Interrupt until resolved to Grade 0 to 1	75% (750 mg/m ²)
2nd appearance		50% (500 mg/m ²)
3rd appearance	Discontinue treatment permanently	-
Grade 4		
1st appearance	Discontinue treatment permanently or, if physician deems it to be in the participant's best interest to continue, interrupt until resolved to Grade 0 to 1	50% (500 mg/m ²)

^a According to the National Cancer Institute of Canada Clinical Trial Group (NCIC CTG) Common Toxicity Criteria (version 1) or the Common Terminology Criteria for Adverse Events (CTCAE) of the Cancer Therapy Evaluation Program, US National Cancer Institute, version 4.0.

Oxaliplatin

Dose Modifications for Neurotoxicity

- For Grade 2 peripheral sensory neuropathy (moderate paresthesia or dysesthesia), or limiting instrumental activities of daily living, skip oxaliplatin. When toxicity resolves to \leq Grade 1, resume oxaliplatin at 75% of initial dose. If oxaliplatin is skipped for 4 weeks (2 consecutive doses) for neurologic toxicity, discontinue oxaliplatin.
- For Grade 3 or greater peripheral sensory neuropathy (severe paresthesia or dysesthesia), or limiting self-care activities of daily living, discontinue oxaliplatin.

Dose Modifications for Participants with Renal Impairment

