7.3.3.3 Dose Modification Criteria for FOLFOX

Recommended dose modifications of FOLFOX are provided in Table 7.3.3.3-1 and criteria for dose modification of FOLFOX are provided in [Table 7.3.3.3-2](#).

Table 7.3.3.3-1: Recommended Dose Modifications of FOLFOX

Drug	Starting Dose	Dose Modification	
		Dose Level - 1	Dose Level - 2
Oxaliplatin	85 mg/m ²	70 mg/m ²	50 mg/m ²
5-FU	Bolus 5-FU: 400 mg/m ² Leucovorin: 400 mg/m ² Infusion 5-FU: 2400 mg/m ² /48 hours	Bolus 5-FU: 300 mg/m ² Leucovorin: 300 mg/m ² Infusion 5-FU: 2000 mg/m ² /48 hours	Bolus 5-FU: 200 mg/m ² Leucovorin: 200 mg/m ² Infusion 5-FU: 1600 mg/m ² /48 hours

Abbreviation: 5-FU: 5-fluorouracil.

Table 7.3.3.3-2: Criteria for Dose Modifications of FOLFOX

Toxicity	Definition	During a course of therapy	Dose adjustments for next treatments
Neutropenia	Grade 3 or greater	Interrupt until resolved to Grade 2	Dose level -1 *If treatment delayed for 4 consecutive weeks, discontinue all treatment
Thrombocytopenia	Grade 2	Interrupt until resolved to Grade 1	Dose level -1 *If Grade 2 persists > 7 days, oxaliplatin reduced by 2 dose levels when platelets improve to Grade 1
	Grade 3	Interrupt until resolved to Grade 1	Dose level -1 *If Grade 3 persists > 7 days, oxaliplatin reduced by 2 dose levels when platelets improve to Grade 1
	Grade 4	Interrupt until resolved to Grade 1	Dose level -1 *If Grade 4 persists > 7 days, oxaliplatin reduced by 2 dose levels when platelets improve to Grade 1
Neurologic toxicity	Grade 2 peripheral sensory neuropathy	Interrupt until resolved to Grade 1	Oxaliplatin dose -1 Continue 5-FU and leucovorin *If oxaliplatin delayed for neurologic toxicity for 4 consecutive weeks, discontinue oxaliplatin, continue 5-FU and leucovorin
	Grade 3 or greater peripheral sensory neuropathy	Discontinue oxaliplatin	Continue 5-FU and leucovorin
Gastrointestinal toxicities	Grade 2 or greater diarrhea	Interrupt until resolved to Grade 1	Dose level -1 If dose delayed for diarrhea for 4 consecutive weeks, discontinue all treatment

For toxicities not listed above, dose modifications are permitted per local standards. Participants may also discontinue oxaliplatin following multiple cycles if, in the investigator’s judgment, cumulative toxicity is likely to increase over time and become problematic.

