Platelets	$< 50000/\text{mm}^3$ (Grade ≥ 3)
AST/ALT	$> \text{ULN} \times 2.5$ (or $> \text{ULN} \times 5.0$ in the presence of liver metastasis)
Serum creatinine	$> \text{ULN} \times 1.2$
Infection	Fever $\geq 38^\circ\text{C}$ suggesting infection

Table 7.3.3.4-2: Criteria of Interruption of Tegafur-Gimeracil-Oteracil Potassium

Parameter	Criteria of Interruption of Tegafur-Gimeracil-Oteracil Potassium (Within the Same Treatment Period)
Diarrhea, stomatitis, Hand-Foot syndrome	Grade \geq 2

Abbreviations: ALT = alanine aminotransferase; AST = aspartate aminotransferase; ULN = upper limit of normal.

Criteria for Dose Reduction of SOX Therapy

On the planned day of administering SOX therapy, it must be confirmed whether the participant fulfills the criteria in Table 7.3.3.4-3. If the participant meets any of the criteria at any time during the last dose and start of subsequent dose, 1 or both agents must be reduced according to Table 7.3.3.4-4 and be continued. Once the dose has been reduced, it should not be increased at a later time.

Table 7.3.3.4-3: Criteria for Dose Reduction of SOX Therapy

Adverse Events		Next Doses	
Parameter	Criteria	Oxaliplatin	Tegafur-Gimeracil-Oteracil Potassium
Decreased platelet count	(only for dose of 130 mg/m ² oxaliplatin) Not met \geq 100000/mm ³ within 7 days of planned date of dosing	1-level reduction	-
	Not met \geq 75000/mm ³ (Grade \leq 1) within 7 days of planned date of dosing		
	(only for dose of 50 mg/m ² oxaliplatin) Not met \geq 75000/mm ³ (Grade \leq 1) within 7 days of planned date of dosing	-	1-level reduction
	< 25000/mm ³ (Grade 4)	1-level reduction	1-level reduction
Decreased neutrophil count	< 500/mm ³ (Grade 4)	1-level reduction	1-level reduction
Febrile neutropenia	Neutrophil count < 1000/mm ³ with fever \geq 38°C (axillary temperature)	1-level reduction	1-level reduction
Diarrhea, stomatitis, Hand-Foot syndrome	Grade \geq 3	1-level reduction	1-level reduction
Allergic reaction/hypersensitivity suspected to be due to	Grade \geq 3	Discontinued	-

Table 7.3.3.4-3: Criteria for Dose Reduction of SOX Therapy

Adverse Events		Next Doses	
Parameter	Criteria	Oxaliplatin	Tegafur-Gimeracil-Oteracil Potassium
administration of oxaliplatin			
Peripheral neuropathy	Grade 2	1-level reduction	-
	Grade 3	Skip dosing ^a	-
	Grade 4	Discontinued	-

^a Resume dosing from 1-level reduction after recovering Grade 2 or less.

Table 7.3.3.4-4: Doses of SOX Therapy for Dose Reduction

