7.4.1 Administration of Study Therapy

The following parameters will be summarized (descriptive statistics) by treatment group. These analyses will be performed on the All Treated LAG-3 Positive Subjects, All Treated LAG-3 Negative Subjects, and All Treated Subjects.

- Relative dose intensity (%) using the following categories: < 50%; 50 - < 70%; 70 - < 90%; 90 - < 110%; ≥ 110%
- Number of doses/cycles received (summary statistics)
- Cumulative dose
- Duration of treatment
 - using a KM curve whereby the last dose date will be the event date for those subjects who are off study therapy. Subjects who are still on study therapy will be censored on their last dose date. Median duration of treatment and associated 95% CI will be provided.

A by-subject listing of dosing of study medication (record of study medication, infusion details, dose change) and a listing of batch number will be also provided.

Key parameters used to characterize dosing data are found in [Table 7.4.1-1](#), [7.4.1-2](#), and [7.4.1-3](#).

Table 7.4.1-1: Administration of Study Therapy for Subjects Treated with XELOX

	BMS-986213 or Nivolumab	Oxaliplatin	Capecitabine
Dosing schedule per protocol	Rela 120mg + Nivo 360mg (BMS-986213) Q3WK, IV or Nivo 360mg Q3WK, IV	130mg/m ² Q3WK, IV	1000mg/m ² Q3WK, oral
Dose*	Dose is defined as Total Dose administered (mg). Dose administered in mg at each dosing date are collected on the CRF	Total dose administered (mg) / most recent BSA	Total dose administered (mg) / most recent BSA
Cumulative Dose	The sum of all doses (mg) administered to a subject during the treatment period	The sum of all doses (mg/m ²) administered to a subject during the treatment period	The sum of all doses (mg/m ²) administered to a subject during the treatment period
Relative Dose Intensity (%)	Cumulative dose (mg) / [Last rela dose date – rela Start dose date + 21] x 120/21] Cumulative dose (mg) / [Last nivolumab dose date – nivolumab Start dose date + 21] x 360/21]	Cumulative dose (mg/m ²) / [Last oxaliplatin dose date – oxaliplatin Start dose date + 21] x 130/21]	Cumulative dose (mg/m ²) / [First dose of capecitabine in the last cycle – capecitabine Start dose date + 21] x 2000/21]
Duration of Treatment	Last dose date (of the last administered study therapy) - Start dose date (of the first administered study therapy) + 1		

* Dose administered in mg at each dosing date and BSA (computed using recent weight and baseline height) are collected on the CRF.

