Table 7.4.1-2: Administration of Study Therapy for Subjects Treated with FOLFOX

	BMS-986213 or Nivolumab	Oxaliplatin	Leucovorin	Fluorouracil
Dosing schedule per protocol	Rela 160mg + Nivo 480mg (BMS-986213) Q4WK, IV or Nivo 480mg Q4WK, IV	85mg/m2 Q2WK	400mg/m2 Q2WK	Bolus 5-FU: 400mg/m2 Q2WK, IV on Day 1 of the cycle Continuous 5-FU: 1200mg/m2 Q2WK, IV continuous infusion on Day1-2 of the cycle
Dose*	Dose is defined as Total Dose administered (mg). Dose administered in mg at each dosing date are collected on the CRF	Total dose administered (mg) / most recent BSA	Total dose administered (mg) / most recent BSA	Total dose administered (mg) / most recent BSA
Cumulative Dose	The sum of all doses (mg) administered to a subject during the treatment period	The sum of all doses (mg/m2) administered to a subject during the treatment period	The sum of all doses (mg/m2) administered to a subject during the treatment period	The sum of all doses (mg/m2) administered to a subject during the treatment period
Relative Dose Intensity (%)	Cumulative dose (mg) / [Last rela dose date – rela Start dose date + 28) x 160/28] Cumulative dose (mg) / [Last nivolumab dose date – nivolumab Start dose date + 28) x 480/28]	Cumulative dose (mg/m2) / [Last oxaliplatin dose date – oxaliplatin Start dose date + 14) x 85/14]	Cumulative dose (mg/m2) / [Last leucovorin dose date – leucovorin Start dose date + 14) x 400/14]	Bolus 5-FU: Cumulative dose (mg/m2) / [First dose of fluorouracil in the last cycle – fluorouracil Start dose date + 14) x 400/14] Continuous 5-FU: Cumulative dose (mg/m2) / [First dose of continuous fluorouracil in the last cycle – continuous fluorouracil Start dose date + 14) x 1200/14]
Duration of Treatment	Last dose date (of the last administered study therapy) - Start dose date (of the first administered study therapy) + 1			

* Dose administered in mg at each dosing date and BSA (computed using recent weight and baseline height) are collected on the CRF.

Table 7.4.1-3: Administration of Study Therapy for Subjects Treated with SOX

	BMS-986213 or Nivolumab	Oxaliplatin	S-1 (tegafur/gimeracil/oteracil)
Dosing schedule per protocol	Rela 120mg + Nivo 360mg (BMS-986213) Q3WK, IV or Nivo 360mg Q3WK, IV	130mg/m ² Q3WK, IV	S-1 (tegafur/gimeracil/oteracil) BID, oral (administered as calculated according to body surface area (BSA, mg/m ² /dose): BSA < 1.25 m ² , 40 mg/dose; ≥1.25 and < 1.5 m ² , 50 mg/dose; ≥1.5 m ² , 60 mg/dose)

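### The XELOX neuropathy stopping rule equates 4 weeks with two oxaliplatin doses, but on the 21-day schedule two doses span 6 weeks

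*Protocol*

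**What the plan says.** Protocol Section 7.3.3.2 deals with Grade 2 peripheral sensory neuropathy on XELOX in three steps. Oxaliplatin is skipped. Once the toxicity has fallen to Grade 1 or less, the site is to "resume oxaliplatin at 75% of initial dose". The limit is then: "If oxaliplatin is skipped for 4 weeks (2 consecutive doses) for neurologic toxicity, discontinue oxaliplatin". The parenthesis presents the time and the dose count as one threshold.

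The XELOX interval is stated consistently elsewhere:

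- Protocol Section 5.1, footnote to the design schematic: oxaliplatin on Day 1 of the regimen's cycle, with capecitabine "administered orally twice daily on Days 1 to 14 of each treatment cycle, every 3 weeks".
- Protocol Section 7.1.2: oxaliplatin "administered IV on Days 1 and 22 of each 6-week treatment cycle".
- SAP Section 7.4.1, XELOX table, relative dose intensity: "oxaliplatin Start dose date + 21] x 130/21", which is a 21-day interval. The FOLFOX table has "oxaliplatin Start dose date + 14) x 85/14", which is a 14-day interval.

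The other two regimens word their neuropathy rules differently. FOLFOX (Protocol Section 7.3.3.3) has a time limit and no dose count: "If oxaliplatin delayed for neurologic toxicity for 4 consecutive weeks, discontinue oxaliplatin". SOX (Protocol Section 7.3.3.4), also every 3 weeks, has neither. Its footnote to the skipped-dose entry reads "Resume dosing from 1-level reduction after recovering Grade 2 or less".

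Three further provisions matter. Section 7.3.1 has treatment resume at the next scheduled time point. Section 7.3.3.1 says omitted doses are not made up, and lets the investigator hold all components for up to 7 days so that they can be given together. Section 8.1 lists the Section 7.3.3.2 criteria among those that require discontinuation.

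**The concern.** On a 21-day schedule, 4 weeks falls between one missed dose and two, so the sentence gives two different limits as if they were one. It also leaves the start of the 4 weeks open. Two sites could read the same mandatory rule and reach different decisions for the same participant: stop oxaliplatin for good after one missed dose, or give it again at 75% of 130 mg/m², which is 97.5 mg/m². Stopping early removes a backbone drug. Stopping late prolongs exposure to a neurotoxic one.

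**Working it through.** **Inputs.** Limit: 4 weeks = 28 days, equated with 2 doses (Section 7.3.3.2). XELOX interval: 21 days (Section 7.1.2; SAP Section 7.4.1). FOLFOX interval: 14 days (Section 7.1.3; SAP Section 7.4.1). Resumption on the dosing grid: Section 7.3.1. Maximum delay of all components: 7 days (Section 7.3.3.1).

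**Step 1: can the plan's equivalence be reproduced?** Two doses × interval:

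- XELOX: 2 × 21 = 42 days = 6 weeks.
- FOLFOX: 2 × 14 = 28 days = 4 weeks.

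Other ways of counting on the 21-day schedule also miss 28:

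| From | To | Days |
|---|---|---|
| First missed slot | Second missed slot | 21 |
| Last dose given | Second missed slot | 42 |
| First missed slot | Slot after two misses | 42 |
| Last dose given | Slot after two misses | 63 |

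The stated figure is not reproduced for XELOX on any of these counts.

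**Step 2: when do the two halves give different decisions?** Call the last dose given Day 1. The slots are then Day 22 (first skip), Day 43 and Day 64. Unless stated otherwise, oxaliplatin counts as skipped until it is next given, and *4 weeks* means 28 days or more.

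*(a) Clock from the first skipped dose, on schedule.* The time limit is 22 + 28 = Day 50.

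- Recovery on Days 23 to 43: resume on Day 43. Elapsed 43 − 22 = 21 days, one dose skipped. Both halves say resume.
- Recovery on Day 44 or later: next slot Day 64. Elapsed 64 − 22 = 42 days, two doses skipped. Both halves say stop.

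No recovery day gives a different decision. This depends on the clock running until the next dose. If it stopped at recovery, recovery on Days 44 to 49 would give 22 to 27 days, short of the time limit, with two doses already skipped.

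*(b) Same clock, one skipped dose, then the 7-day delay of all components.* Resumption on 43 + 7 = Day 50. Elapsed 50 − 22 = 28 days, one dose skipped. The time limit says stop and the dose count says resume. Delays of 3 to 6 days give 24 to 27 days and no conflict.

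*(c) Clock from onset of the Grade 2 neuropathy, one skipped dose, resumption on Day 43.* The time limit is reached if onset was on or before 43 − 28 = Day 15. The dose count (one) still says resume. Onset on Day 16 or later gives no conflict.

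*(d) Clock from the last dose given.* The time limit is 1 + 28 = Day 29, after one skipped dose.

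- Clock runs to the next dose: recovery on Days 23 to 43 leads to resumption on Day 43, with 42 days elapsed and one dose skipped. The halves conflict on 43 − 23 + 1 = 21 recovery days.
- Clock stops at recovery: recovery on Days 23 to 28 is inside the limit, so the conflict is confined to Days 29 to 43, which is 43 − 29 + 1 = 15 recovery days.

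Where the halves conflict in (b) to (d), the choice is between no further oxaliplatin and 0.75 × 130 = 97.5 mg/m².

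**The case against.** The strongest reply is that the wording is loose but the rule works. A dose that was given has not been skipped, so the natural clock starts at the first skipped dose, and on schedule the two halves then agree. The last-dose clock is strained: if it runs to the next dose, nobody on schedule who skipped a dose could ever resume, which cancels the instruction to restart at 75%. Sections 7.3.3 and 7.3.3.1 also allow chemotherapy changes per local standard, and Table 2-2 lets later XELOX doses follow local windows.

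Most of this stands, and it is why the point is minor. It does not dispose of it. The 7-day hold is expressly permitted and reaches exactly 28 days on the natural clock with one dose skipped. A clock from toxicity onset is not excluded by the text. Local latitude softens how the rule is applied but does not say what the threshold is, and Section 8.1 makes it a mandatory criterion.

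A reader might infer more than the documents support:

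- **That the sentence was carried over from FOLFOX.** The arithmetic fits the 14-day interval, but the FOLFOX rule has no dose count, and nothing shows where the XELOX sentence came from or which half was meant.
- **That XELOX participants will routinely lose oxaliplatin one dose too soon.** This needs the strained last-dose clock, or one of the specific circumstances in (b) and (c).
- **That the limit contradicts the general 6-week and 42-day limits in Sections 7.3.3.1 and 7.3.4.** Those run on different clocks, so no conflict or alignment with them is claimed.
- **That the treatment comparison is biased.** The same rule applies in both arms.

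**Conclusion.** The two halves of the XELOX threshold are not equivalent: two doses span 6 weeks, not 4. With on-schedule dosing, and the clock running from the first skipped dose to the next dose given, this changes no decision. The halves conflict in three situations:

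- one skipped dose followed by the full 7-day hold, if exactly 28 days triggers the limit and the hold counts as time skipped for neuropathy;
- a clock from toxicity onset, with onset at least 28 days before the resumption slot;
- less plausibly, a clock from the last dose given, with 15 to 21 discordant recovery days.

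The scope is XELOX participants with Grade 2 peripheral sensory neuropathy. The documents give no expected number, so the count affected cannot be estimated. Sample size, alpha and the ORR analysis are unaffected. It is a minor correction, worth making because a mandatory stopping criterion should have one meaning.

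**What to change.** Make the dose count the sole trigger in Section 7.3.3.2 and delete the week limit, for example: *Discontinue oxaliplatin once two consecutive scheduled doses have been skipped because of neurologic toxicity.*

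If the clinical team intends a 4-week limit instead, delete the dose count and state three things: that the 4 weeks run from the due date of the first skipped dose, that they end when oxaliplatin is next given (if so intended), and whether exactly 28 days, including a 7-day hold under Section 7.3.3.1, triggers discontinuation. The two options agree for on-schedule dosing with the clock in (a), but can differ at Day 50 after a 7-day hold, so the team should choose between them deliberately.

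Cost: an administrative letter or a one-sentence protocol clarification. No change to the SAP, the analysis or the sample size.
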